**Table 5 Schedule of Screening and Treatment Period Procedures**

| Procedure    | Screening            | Treatment Period: Up to 12 Months
28-day Cycles |                     |                     |                     |                          |
|--------------|----------------------|--|---------------------|---------------------|---------------------|--------------------------|
|              |                      | Cycle 1  | Cycle 2             | Cycle 3             | Cycle 4             | Cycle 5 through Cycle 13 |
|              | Day -28 to
Day -1 | Day 1  | Day 1
(± 3 days)      |
| c |                      |  |                     |                     |                     |                          |

- c Tumor tissue sample, when available, from the original diagnosis and before initiation of chemoradiotherapy will be collected at screening, per inclusion criterion. Optional fresh tumor tissue specimens may be collected after completion of chemoradiotherapy during screening and on treatment at the time of the PET/CT (Cycle 7). Additional on-treatment fresh tumor tissue specimens may be collected at the investigator's discretion as clinically indicated for correlative biomarker studies. See Section [4.3.7.4](#).
- d If screening laboratory assessments are performed within 3 days prior to Day 1, they do not need to be repeated at Day 1.
- e TSH, T3, and T4. If TSH is normal, then T3 or T4 is not required. Free T3/free T4 are preferred over total T3/total T4.
- f Females of childbearing potential are required to have a pregnancy test within 7 days prior to the first dose of study treatment. A urine or serum pregnancy test is acceptable; if urine test is equivocal or positive then serum β-hCG testing should be performed for confirmation.
- g Active hepatitis B, hepatitis C, and HIV infections are defined by positive serologic test. Subjects positive for HBV infection are eligible if findings are compatible with past or resolved infection (HBsAg negative, anti-HBc positive and anti-HBs positive) or due to vaccination (HBsAg negative, anti-HBc negative and anti-HBs positive). Subjects positive for HCV antibody are eligible only if polymerase chain reaction is negative for HCV RNA.
- h Screening disease assessment and brain MRI or CT must be performed after completion of chemoradiotherapy.
- i In combination arms, PK predose (within 1 hour prior to dosing) and EOI (within 15 minutes post-EOI) samples will be collected according to the administration time of each study drug. For example: PK predose Agent 1 collected → Agent 1 administration → PK EOI Agent 1 collected → PK predose Agent 2 collected → Agent 2 administration → PK EOI Agent 2 collected.
- j In combination arms, at visits when predose samples only are required, PK samples will be collected within 1 hour prior to administration of the first study drug only. For example: PK predose Agent 1 and Agent 2 collected → Agent 1 administration → Agent 2 administration.
- k In combination arms, ADA samples will be collected within 1 hour prior to administration of the first study drug only. For example: ADA predose Agent 1 and Agent 2 collected → Agent 1 administration → Agent 2 administration.
- l Treatment regimens are described in Section [3.1.2](#).

#### 4.2.2 Follow-up Period

**Table 6** presents follow-up procedures for subjects who completed study treatment and maintain DC, subjects who discontinued study treatment due to other reason not related to PD (Section 4.1.6), and subjects who experienced unconfirmed PD and are eligible for a confirmation scan. Procedures for subjects who discontinue study treatment due to PD are provided in Section 4.2.3. Overall, all subjects continuing in the study must adhere to the study procedures for up to 5 years (from randomization) provided they achieve DC and remain disease free.

As OS is a late endpoint in this patient population, after the planned 5-year post randomization study period, subjects may be contacted for survival every 12 months.

**Table 6 Schedule of Follow-up Procedures: Subjects Who Completed Study Treatment and Maintain DC, Subjects Who Discontinued Study Treatment Due to Other Reason Not Related to PD, and Subjects Who Experienced Unconfirmed PD and are Eligible for a Confirmation Scan**

| Time since Cycle 1 Day 1                    | ≤ 12 Months                          | > 12 to ≤ 24 Months               | > 24 to 60 Months             |
|---|--------------------------------------|-----------------------------------|-------------------------------|
| Follow-up based on previous scheduled visit | Every 8 Weeks
(± 3 days)          | Every 12 Weeks
(± 7 days)      | Every 6 Months
(± 4 weeks) |
| Procedure                            |                                      |                                   |                               |
| Physical examination                        | X                                    | X                                 | X                             |
| Vital signs                                 | X                                    | X                                 | X                             |
| ECOG performance status                     | X                                    | X                                 | X                             |
| Serum chemistry                             | X                                    | X                                 | X                             |
| Thyroid function tests a         | X                                    | X                                 | X                             |
| Hematology                                  | X                                    | X                                 | X                             |
| Concomitant medications b        | X                                    | X (up to Month 15, if applicable) |                               |
| Assessment of AEs/SAEs b         | X                                    | X (up to Month 15, if applicable) |                               |
| Disease assessment (scans)                  | X
(within 7 days)                 | X                                 | X                             |
| CCI   |                                      |                                   |                               |
|   |                                      |                                   |                               |
| Serum for PK                                | 10 months post
Cycle 1 Day 1 only | Month 15 only                     |                               |

**Table 6 Schedule of Follow-up Procedures: Subjects Who Completed Study Treatment and Maintain DC, Subjects Who Discontinued Study Treatment Due to Other Reason Not Related to PD, and Subjects Who Experienced Unconfirmed PD and are Eligible for a Confirmation Scan**

| Time since Cycle 1 Day 1  | ≤ 12 Months                       | > 12 to ≤ 24 Months          | > 24 to 60 Months             |
|---|-----------------------------------|------------------------------|-------------------------------|
| Follow-up based on previous scheduled visit   | Every 8 Weeks
(± 3 days)       | Every 12 Weeks
(± 7 days) | Every 6 Months
(± 4 weeks) |
| Procedure  |                                   |                              |                               |
| Serum for ADA   | 10 months post Cycle 1 Day 1 only | Month 15 only                |                               |
| Survival status (if visits are discontinued, this may be done via telephone contact) c | X                                 | X                            | X                             |

ADA = antidrug antibody; AE = adverse event; CCI [REDACTED]; DC = disease control; ECOG = Eastern Cooperative Oncology Group; PD = progressive disease; PK = pharmacokinetics; SAE = serious adverse event; T3 = triiodothyronine; T4 = thyroxine; TSH = thyroid stimulating hormone.

- a TSH, T3, and T4. If TSH is normal, then T3 or T4 is not required. Free T3/free T4 are preferred over total T3/total T4.
- b Concomitant medications and AEs/SAEs will be collected up to 12 months post Cycle 1 Day 1, regardless of whether the subject discontinued treatment. Following the first 12 months, concomitant medications and AEs/SAEs will be collected up to 3 months post last dose of study treatment, if applicable.
- c Subjects may be contacted for survival status every 12 months beyond 60 months post Cycle 1 Day 1, until the end of the entire study, unless the subject withdraws consent from further participation in the study.

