| Serum chemistry                     | X                    | X d                                     | X                        | X                        | X                        | X  |
| Hematology                          | X                    | X d                                     | X                        | X                        | X                        | X  |
| Urinalysis                          | X                    | As clinically indicated                            |                          |                          |                          |  |
| Thyroid function tests e | X                    | X d                                     | X                        | X                        | X                        | X  |
| Pregnancy test f         | X                    | X  | X                        | X                        | X                        | X  |
| Coagulation parameters              | X                    |  |                          |                          |                          |  |
| Hepatitis B and C; HIV g | X                    |  |                          |                          |                          |  |
| Concomitant medications             | X                    | X  | X                        | X                        | X                        | X  |
| Assessment of AEs/SAEs              | X                    | X  | X                        | X                        | X                        | X  |
| Disease assessment (scans)          | X h       |  |                          | X
(within 7 days)     |                          | Cycle 5 then every 2 cycles
(within 7 days) |

**Table 5** Schedule of Screening and Treatment Period Procedures

| Procedure                              | Screening         | Treatment Period: Up to 12 Months
28-day Cycles |                          |                          |                          |   |
|--|-------------------|--|--------------------------|--------------------------|--------------------------|---|
|  |                   | Cycle 1  | Cycle 2                  | Cycle 3                  | Cycle 4                  | Cycle 5 through Cycle 13                            |

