#### **4.8.7 Interim Analysis**

Interim analyses will be conducted during the course of the study to evaluate the clinical activity and safety of any experimental arm in comparison with the control arm. The results of the interim analyses may be used for internal program decision and/or potential interactions with regulatory agencies on future development. The first interim analysis will be performed once the control arm has 30 ITT subjects who have reached the data cutoff criteria (defined as the opportunity to be followed for at least 16 weeks at the time of data cutoff). The DCR at Week 16 will be used for No-Go decision, and ORR may be used for early Go decision. Enrollment will not be paused for interim analyses.

Bayesian PP will be used to evaluate clinical activity ([Lee and Liu, 2008](#)). [Table 10](#) illustrates the sample algorithm to make a No-Go decision based on DCR at 16 weeks at the interim analysis when the control arm and an experimental arm each have 30 subjects. If an early No-Go decision is made, enrollment to the corresponding experimental arm will be stopped. In

this study, we assume a target value (TV) of  $\Delta$ DCR at 16 weeks as 15%, where  $\Delta$ DCR is the difference in DCR between an experimental arm and control arm.

- An experimental arm will meet the No-Go criteria if the probability that the true  $\Delta$ DCR is larger than TV is less than 10%, ie,  $\text{Prob.}(\text{True } \Delta\text{DCR} > 0.15) < 0.10$ . A No-Go decision will be made at an interim analysis if the PP of meeting the No-Go criteria given observed data is greater than 95%, ie,  $\text{PP}[\text{Prob.}(\Delta\text{DCR} > 0.15) < 0.10] > 0.95$ .

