**Table 3.4.1      Summary of Censoring Guidelines for PFS**

Situation	Date of PD/Death or Censoring	PFS Outcome
Documented Progressive Disease (PD) or death	Date of earliest sign of PD or death, whichever comes first	Event (unless the censoring rule specified below)
Death or PD immediately after $\geq 2$ consecutive missed or non-evaluable disease assessments as per the protocol specified assessment schedule	Date of last progression-free disease assessment prior to missed or non-evaluable assessments, or randomization, whichever occurred last	Censored
No PD or death at time of analysis or lost to follow-up	Date of last evaluable progression-free disease assessment	Censored
No tumor assessment at baseline and no evidence of PD at first post-baseline disease assessment OR No tumor assessment post-first dose, and no death prior to second scheduled post-baseline disease assessment	Date of randomization	Censored

PD = progressive disease; PFS = progression-free survival.

Subjects having missing lesion data at baseline or no disease assessments post-first dose of IP will have PFS censored at the date of randomization unless the subject dies prior to the second scheduled post-baseline disease assessment in which case the death date will qualify as a PFS event.

If a subject has two or more consecutive completely missed or non-evaluable assessments followed immediately by death or an assessment showing radiologic disease progression, then the subject will be censored for PFS. PFS will be censored at the date of randomization or the last progression-free disease assessment prior to the missed or non-evaluable assessments, whichever occurred last.

If a subject has two or more consecutively missed or non-evaluable assessments followed by an assessment showing no radiologic disease progression, then the assumption will be that the subject did not progress during the missed or non-evaluable assessments.

The length of gap (in number of days) to determine two or more consecutive assessments is defined as the following:

- 126 days during the first 12 months (A 8-week disease assessment interval plus a 7-day window for each assessment).

- 182 days from month 12 to month 24 (A 12-week disease assessment interval plus a 7-day window for each assessment).
- 422 days after month 24 (A 6-month disease assessment interval plus a 4-week window for each assessment).

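### Off-treatment scans in year 1 are timed from the last visit, not the last scan, so an even-cycle stop leaves a 12-week gap and one missed scan can exceed the SAP's 126-day limit for two

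*Protocol*

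**What the plan says.** Protocol Table 5 (section 4.2.1) uses 28-day cycles with a visit on Day 1 of each. Scans are due at Cycle 3 and then "Cycle 5 then every 2 cycles", which is weeks 8, 16, 24, 32, 40 and 48 from Cycle 1 Day 1.

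Protocol Table 6 (section 4.2.2) covers subjects who are off treatment without progression. Its timing rule is "Follow-up based on previous scheduled visit". The interval is 8 weeks up to 12 months from Cycle 1 Day 1, then 12 weeks to month 24, and scans are done at these visits. Nothing ties the scans back to the date of the last scan.

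SAP section 3.4.2.4 censors PFS when progression or death comes straight after two or more consecutive missed or non-evaluable assessments. Table 3.4.1 counts those misses against the protocol's assessment schedule. The text below the table converts the count to days. For year 1 it gives "126 days during the first 12 months (A 8-week disease assessment interval plus a 7-day window for each assessment". Built the same way, the limit is 182 days in the second year and 422 days thereafter. If the next scan is free of progression, nothing is censored.

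Protocol section 4.8.7 states: "The DCR at Week 16 will be used for No-Go decision". The SAP interim section admits subjects first dosed at least 16 weeks before the cutoff.

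**The concern.** The on-treatment visit grid (4 weeks) is finer than the scan grid (8 weeks). Restarting an 8-week clock at the last visit therefore shifts the scan grid by 4 weeks for anyone who stops after an even-numbered cycle, even when every dose and visit was on time. The SAP's 126-day limit assumes an unbroken 8-week scan interval through year 1.

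Two things are at stake. The first is whether some progressions and deaths count as PFS events or are censored. The second is whether stable disease lasting 16 weeks can be shown in time for an interim look. Both then depend on the cycle at which treatment stopped, and stopping can differ between arms in an open-label study of added agents.

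**Working it through.** **The SAP limits.** Limit = 2 × (interval + window).
- Year 1: 2 × (56 + 7) = 126 days.
- Months 12 to 24: 2 × (84 + 7) = 182 days.
- After month 24: 2 × (183 + 28) = 422 days.

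All three reproduce the SAP.

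**How the limit behaves on the Table 5 grid.** One missed scan gives 112 days (98 to 126 with ±7-day scan windows), never above 126. Two missed give 168 days (154 to 182), always above 126. On that grid the rule separates one miss from two.

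**Scan dates under Table 6.** The last visit at Cycle c is at week 4(c − 1). Off-treatment scans follow every 8 weeks, or every 12 weeks once an 8-week step would pass 12 months. Gaps are in days. For Cycle 2 they are counted from Cycle 1 Day 1, since no post-baseline scan exists yet.

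| Last visit | Week | Last scan (week) | Next scans (weeks) | First gap | Gap if first is missed |
|---|---|---|---|---|---|
| Cycle 2 | 4 | none | 12, 20, 28 | 84 | 140 |
| Cycle 3 | 8 | 8 | 16, 24, 32 | 56 | 112 |
| Cycle 4 | 12 | 8 | 20, 28, 36 | 84 | 140 |
| Cycle 6 | 20 | 16 | 28, 36, 44 | 84 | 140 |
| Cycle 8 | 28 | 24 | 36, 44, 52 | 84 | 140 |
| Cycle 10 | 36 | 32 | 44, 52, 64 | 84 | 140 |
| Cycle 11 | 40 | 40 | 48, 60, 72 | 56 | 140 |
| Cycle 12 | 44 | 40 | 52, 64, 76 | 84 | 168 |
| Cycle 13 | 48 | 48 | 60, 72, 84 | 84 | 168 |

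For example, after a Cycle 4 stop the first gap is (20 − 8) × 7 = 84 days, and with the week-20 scan missed it is (28 − 8) × 7 = 140 days.

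- For even cycles 2 to 10, 140 days becomes 126 to 154 with scan windows. It exceeds 126 in 224 of the 225 combinations of whole-day shifts.
- For Cycles 11 to 13, the 140 or 168 days cross month 12 and lie between 126 and 182. The SAP does not say which limit applies.
- Only stops after Cycle 2 or 4 lose the week-16 scan. Later even-cycle stoppers had it at Cycle 5.

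**Early No-Go.** I took SAP Table 4.1 with 30 subjects per arm and control DCR 60%. P(early No-Go) is the sum, over control counts from 10 to 30, of the binomial probability of that count times the binomial probability that the experimental count is at or below the tabled bound. At true gains of 0, 5, 10 and 15 points this gives 18.9%, 10.5%, 5.1% and 2.2%. SAP Table 4.2 has 19%, 11%, 5% and 2%.

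A lost subject is then fixed as a failure, leaving 29 (or 28) binomial outcomes in that arm.

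| Lost | True gain 10 points | True gain 15 points |
|---|---|---|
| None | 5.1% | 2.2% |
| One, experimental arm only | 7.0% | 3.2% |
| Two, experimental arm only | 9.4% | 4.6% |
| One in each arm | 4.7% | 1.9% |
| Two in each arm | 4.3% | 1.7% |

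**How many could be lost.** The documents give no rate of stopping before week 16 for reasons other than progression. Assume 5 to 10%, spread evenly over Cycles 1 to 4. Half fall at even cycles, so 2.5 to 5%, or 0.75 to 1.5 of 30. Only those between weeks 16 and 20 at cutoff are exposed. If that is 15 to 33% of subjects (also an assumption, as no accrual rate is given), the number is 0.75 × 0.15 = 0.11 to 1.5 × 0.33 = 0.5. Of these, only subjects with stable disease matter.

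**The case against.** The strongest reply concerns the consequences, and much of it stands.

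- A reader might infer that every even-cycle stop loses the week-16 scan. Only Cycles 2 and 4 do.
- A reader might infer that these subjects count as interim failures whatever their disease state. They do not: disease control includes response, and the SAP's No-Go interim accepts unconfirmed responses. A week-20 scan showing stable disease also supports 16-week control later.
- A reader might infer that the schedule biases No-Go against the experimental arm. The documents give no arm difference in such stops, and equal loss lowers early No-Go slightly. An opposite effect also exists: after a Cycle 4 stop, a progression arising in weeks 8 to 16 is first dated about week 20 and might pass as disease control.
- A reader might infer that any single missed scan leads to censoring. In the even-cycle pattern it must be the first off-treatment scan, and progression or death must come next. A missed later scan within year 1 gives 112 days.
- Table 6 could be read as meaning the previous scan visit, and extra scans are allowed when clinically indicated. A subject who attends Cycle 5 Day 1 undosed would get the week-16 scan. But Table 6 does not name the scan as its anchor, and discretionary scans do not repair a schedule.
- The Amendment 4 summary says all subjects have completed treatment. A Table 6 change therefore recovers nothing for current subjects.

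None of this removes the 84-day gap, or the conflict inside SAP 3.4.2.4 between counting scheduled misses and counting days.

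**Conclusion.** The point holds and is minor. Read as written, Table 6 gives an 84-day first scan gap after any even-cycle stop, against 56 days on the Table 5 grid. After a stop at even cycles 2 to 10, missing only the first off-treatment scan gives 140 days. The day rule then treats that as two misses and censors a progression found next, whereas Table 3.4.1 counts one miss and keeps the event. The same applies to a death next, if it falls more than 126 days after the last scan. The exception is a subject with no post-baseline scan who dies before the second scheduled one, whom the SAP keeps as an event.

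The number of PFS events affected cannot be estimated from the documents.

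The interim effect is confined to stable-disease subjects who stopped after Cycle 2 or 4 and are between weeks 16 and 20 at cutoff. Under the assumptions above that is at most about half a subject of 30. The documents do not support a claim that the No-Go rule is materially biased.

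The result assumes that the previous scheduled visit is the last attended Day 1 visit in Table 5, and that the subject does not attend the next odd-cycle visit.

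**What to change.** 1. **SAP 3.4.2.4, for existing data.** Replace the fixed 126-day gap with a count of missed or non-evaluable assessments against each subject's actual Table 5 and Table 6 schedule, so that one missed scan after an even-cycle stop is not censored as two. State which limit applies to a gap that crosses month 12. This costs one paragraph and a derivation of scheduled scan dates per subject.

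2. **Protocol Table 6, for any subjects or arms still to be treated.** Tie disease assessments in the first 12 months to the Table 5 calendar from Cycle 1 Day 1 (weeks 8, 16, 24, 32, 40 and 48, within 7 days), whatever the last on-treatment visit. This is a one-line change. It keeps the week-16 scan and restores the grid on which 126 days separates one miss from two. The cost is that some off-treatment visits fall 4 weeks after the last one, with at most one more scan in year 1 for even-cycle stoppers.

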#### 4.2.3 End of Study

**Table 7** presents procedures for the end of study visit for all subjects. End of study visit will be performed when a subject discontinues study due to a confirmed PD, or a subject experienced an unconfirmed PD but is not eligible for a confirmation scan, or after 60 months of follow-up for subjects who achieve DC and remain disease free, or at the last study visit for subjects who discontinue study due to reason not related to PD.

Subjects who discontinue treatment due to any reason, including confirmed PD or initiation of alternative anticancer therapy, will be followed for survival according to the timepoints in **Table 6** (every 8 weeks up to 12 months post Cycle 1 Day 1, every 12 weeks from > 12 to ≤ 24 months, and every 6 months from > 24 to 60 months post Cycle 1 Day 1) unless the subject withdraws consent from further participation in the study. After 60 months, subjects may be contacted for survival every 12 months until the end of the entire study.

